**Inclusion criteria:**

- Male and female patients at least 18 years old
- Patients with confirmed pituitary origin of excess adrenocorticotrophic hormone (ACTH) production:
  - Persistent hypercortisolemia established by two consecutive 24 hr UFC levels at least 1.5x the upper limit of normal
  - Normal or elevated ACTH levels
  - Pituitary macroadenoma ( $>1$  cm) on MRI OR
  - Inferior Petrosal Sinus Sampling (IPSS) central to peripheral ACTH gradient  $>2$  at baseline and  $>3$  after CRH stimulation
  - Recurrent or persistent Cushing disease is defined as pathologically confirmed resected pituitary ACTH-secreting tumor, and 24 hour UFC above the upper limit of normal reference range beyond post-surgical week 6
  - Patients on medical treatment for Cushing's disease the following washout periods must be completed before screening assessments are performed :
    - Inhibitors of steroidogenesis (metyrapone, ketoconazole): 2 weeks
    - Somatostatin analogs (pasireotide): 2 weeks
    - Progesterone receptor antagonist (mifepristone): 2 weeks

- Dopamine agonists (cabergoline): 4 weeks
- CYP3A4 strong inducers or inhibitors: varies between drugs; minimum 5-6 times the half-life of drug

*Exclusion criteria:*

- Patients with compromised visual fields, and not stable for at least 6 months
- Patients with abutment or compression of the optic chiasm on MRI and normal visual fields
- Patients with Cushing's syndrome due to non-pituitary ACTH secretion
- Patients with hypercortisolism secondary to adrenal tumors or nodular (primary) bilateral adrenal hyperplasia
- Patients who have a known inherited syndrome as the cause for hormone over secretion (i.e. Carney Complex, McCune-Albright syndrome, MEN-1)
- Patients with a diagnosis of glucocorticoid-remedial aldosteronism (GRA)
- Patients with cyclic Cushing's syndrome defined by any measurement of UFC over the previous 1 months within normal range
- Patients with pseudo-Cushing's syndrome, i.e. non-autonomous hypercortisolism due to overactivation of the HPA axis in uncontrolled depression, anxiety, obsessive compulsive disorder, morbid obesity, alcoholism, and uncontrolled diabetes mellitus
- Patients who have undergone major surgery within 1 month prior to screening
- Patients with serum  $K^+ < 3.5$  while on replacement treatment
- Diabetic patients whose blood glucose is poorly controlled as evidenced by  $HbA1C > 8\%$

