- Patients who were receiving mitotane and/or long-acting somatostatin analogs (octreotide LAR or lanreotide)
- Patients who were receiving pasireotide or ketoconazole before study entry must complete a 2 week washout period prior to receiving seliciclib
- Patients who have received pituitary irradiation within the last 5 years prior to the baseline visit
- Patients who have been treated with radionuclide at any time prior to study entry
- Patients with known hypersensitivity to seliciclib
- Patients with a history of non-compliance to medical regimens or who are considered potentially unreliable or will be unable to complete the entire study
- Patients with presence of Hepatitis B surface antigen (HbsAg)
- Patients with presence of Hepatitis C antibody test (anti-HCV)

*Withdrawal of Subjects:*

- Monitoring for adverse effects: Patients will be evaluated for adverse effects weekly with physical examinations, chemistry and hematology panels. Adverse events will be graded by the NCI-CTCAE and include: fatigue, fever, nausea, vomiting, anorexia, hepatic dysfunction (increased ALT/SGPT, AST/SGOT and AP), hypokalemia, hyponatremia and insomnia [IND No. 71,011-CYC202(R-roscovitine or Seliciclib)]. Seliciclib will be discontinued in those who developed worsening of visual fields, and those with toxicity greater than or equal to Grade 4 on the NCI-CTCAE. Demonstration of compromised visual fields at any time will lead to withdrawal from the study and surgical referral.

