## Section 6.0 Treatment of Subjects

Transsphenoidal pituitary tumor resection is the primary therapy for Cushing disease, and yields 30-70% surgical cure rates. Patients with recurrent or residual tumors, and/or are not surgical candidates typically undergo pituitary-directed radiation, adrenalectomy, treated with pasireotide, and/or medical suppression of adrenal gland cortisol production. In this study, we will treat patients with *de novo*, persistent, or recurrent Cushing disease with seliciclib during the period of evaluation and preparation for standard care, which usually takes 4 weeks at our center. We are excluding any subjects who need immediate surgical intervention, i.e. unstable visual field deficit, tumor compression of optic chiasm, or severe metabolic complications. We only will recruit those whom we would recommend for routine evaluation process for standard care. After completion of their participation in the study, subjects will be ready to start standard care. If a given patient responds to the study drug and chooses to stay on the drug after cessation of the trial, clinical data will continue to be collected for further analysis of drug response and monitoring safety.

Study calendar: baseline physical exam, vital signs, weight and laboratory evaluations will be conducted within 7 days prior to the start of therapy. Pituitary imaging and ECG will be performed within 60 days prior to the start of therapy. All procedures and evaluations may be performed within 3 calendar days of that specified in the protocol to accommodate patient convenience and scheduling. Patient informed consent will be obtained prior to any protocol-specific procedures. The schedule of study events is provided in Table 1.

Patients will be administered a dose of oral seliciclib 400 mg twice daily for 4 days every week for total of 4 weeks. Patients will be seen on days 1, 8, 15, 22 and 29 for repeat laboratory testing, assessment of treatment compliance, and toxicity according to National Cancer Institute Common Toxicity Criteria version 3.

The following tests will be performed:

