### ***Monitoring for adverse effects (further detailed below):***

- Patients will be seen in clinic every week and evaluated for adverse effects with physical exam, ECG, chemistry, hematology panels, as listed in Table 1. Adverse events will be graded according to NCI Common Terminology Criteria (NCI-CTCAE). Known common adverse events of R-roscoxitine at 400mg oral dose twice daily include fatigue, fever, nausea, vomiting, anorexia, hepatic dysfunction (increased ALT/SGPT, AST/SGOT and AP), hypokalemia, hyponatremia, anemia and insomnia (cross reference: IND No. 71,011-CYC202(R-roscoxitine or Seliciclib)).
- 
- If at any time a patient demonstrates a worsening of their visual fields or tumor growth on MRI, they will be withdrawn from the study and referred for surgery.
- All patients will be followed regularly until the resolution or stabilization of drug-related toxicity. A post-treatment follow-up visit will be conducted within 4 weeks after the last dose of the study drug or prior to the initiation of new treatment. This post-treatment evaluation may be conducted over the telephone if the patient is unable to return to the clinic.
- In all cases where the subject is withdrawn due to unusual or unusually severe adverse event considered related to R-roscoxitine, the withdrawal will be reported as an SAE and on the CRFs.

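### The visual rules conflict: Section 5 does not exclude chiasm compression with a stable field defect, Section 6 does, and the withdrawal statements disagree on stable defects

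*Combined protocol and SAP*

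**What the plan says.** Two lines in the Section 5.0 exclusion list concern vision. One excludes "Patients with compromised visual fields, and not stable for at least 6 months". The other excludes "Patients with abutment or compression of the optic chiasm on MRI and normal visual fields". Each carries a second condition.

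Section 6.0 restates who is kept out: "We are excluding any subjects who need immediate surgical intervention, i.e. unstable visual field deficit", continuing with "tumor compression of optic chiasm, or severe metabolic complications". Here compression carries no condition on the fields, and abutment is not mentioned.

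Three statements govern what happens to a patient in the study:

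- Section 5.0, Withdrawal of Subjects: "Seliciclib will be discontinued in those who developed worsening of visual fields".
- The same bullet, last sentence: "Demonstration of compromised visual fields at any time will lead to withdrawal from the study and surgical referral".
- Section 8.0, Monitoring for adverse effects, sets withdrawal and referral for surgery for this case: "If at any time a patient demonstrates a worsening of their visual fields or tumor growth on MRI".

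Visual fields are tested at the screening visit, at baseline visit 1 (Day -7) and at Visit 6 (Day 29). Section 7.0 limits the primary efficacy population to patients who completed the 4-week treatment period with no more than 2 weeks of interrupted dosing.

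**The concern.** Eligibility is normally checked line by line against the exclusion list. The chiasm line applies only when the fields are normal, and the field line applies only when the defect has not been stable. A patient with both compression and a long-stable defect therefore passes the list, although Section 6.0 describes compression as a reason for exclusion.

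The second difficulty concerns the 6-month stability condition. It implies that some patients with a stable defect may enter. The last sentence of the withdrawal bullet depends on the presence of a defect, not on change, and makes no exception for one that was already there. Taken at its word, it removes a patient whom the exclusion list has just allowed. The other two statements would keep that patient.

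What is at stake is consistent handling at a safety boundary. Two staff members applying different parts of the same protocol could reach opposite decisions on entry or withdrawal for the same patient. In a 16-patient single-arm trial those decisions also determine who is counted for the primary outcome.

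**Working it through.** The question is one of logic, so the check is an enumeration. It crosses three chiasm states (none, abutment, compression) with three field states (normal, defect stable for at least 6 months, defect not stable) and applies each rule literally.

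Rules used:

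- Section 5.0 excludes if the defect is not stable, or if there is abutment or compression with normal fields.
- Section 6.0 excludes if the defect is not stable, or if there is compression.
- The last sentence of the withdrawal bullet applies if the field is not normal.
- The two worsening statements apply to no cell at entry, because each requires a change.

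| Chiasm | Fields | Excluded, Section 5.0 | Excluded, Section 6.0 | Meets last withdrawal sentence |
|---|---|---|---|---|
| None | Normal | No | No | No |
| None | Stable defect | No | No | Yes |
| None | Unstable defect | Yes | Yes | Yes |
| Abutment | Normal | Yes | No | No |
| Abutment | Stable defect | No | No | Yes |
| Abutment | Unstable defect | Yes | Yes | Yes |
| Compression | Normal | Yes | Yes | No |
| Compression | Stable defect | No | Yes | Yes |
| Compression | Unstable defect | Yes | Yes | Yes |

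Results:

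1. Compression with a stable defect is the only cell that Section 5.0 admits and Section 6.0 excludes.
2. All three stable-defect cells are admitted by Section 5.0 but meet the last withdrawal sentence. Under the worsening-based sentence before it, and under Section 8.0, none of the three would be withdrawn unless the field changed.
3. There is one mismatch in the other direction: abutment with normal fields is excluded by Section 5.0 but not named in Section 6.0.

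Timing: because fields are tested at screening and baseline, a pre-existing defect would be documented before the first dose. Under the last withdrawal sentence alone, the condition would then already be met.

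Effect on the design: Section 9.0 plans 16 patients, with success at 3 or more responders and response rates of 5% (null) and 25% (alternative). The probability of success is 1 − Σ(k=0 to 2) C(n,k) p^k (1−p)^(n−k). For n = 16 this gives 0.0429 at p = 0.05 and 0.803 at p = 0.25, in line with the stated one-sided 0.05 level and 80% power. The wording conflict changes none of these figures.

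If an admitted patient were withdrawn, counted among the 16 and not replaced, and the cut stayed at 3, power at p = 0.25 would be:

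- n = 15: 1 − (0.0134 + 0.0668 + 0.1559) = 0.764
- n = 14: 1 − (0.0178 + 0.0832 + 0.1802) = 0.719

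The documents establish neither that such a patient counts among the 16 nor that there is no replacement. These two figures are conditional illustrations of losing any patient, not a consequence of this conflict.

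**The case against.** The strongest reply is that the protocol read as a whole settles the matter. Section 6.0 is operative text, so a site that applies it would not enroll a patient with compression. Alternatively, its list is governed by its opening condition of needing immediate surgery, in which case a stable patient may fall outside it and there is no contradiction with Section 5.0. Section 5.0 also excludes patients who will be unable to complete the study, which could catch someone bound to be withdrawn. Section 6.0 further limits recruitment to patients suited to routine evaluation for standard care.

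These arguments do not remove the conflict. The first two give opposite answers for the same patient, and the text does not say which applies. The inability-to-complete line helps only if the unconditional withdrawal sentence is the governing one, which is itself in dispute. The routine-evaluation sentence leaves to discretion what the exclusion list tries to specify.

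One part of the reply does stand. The unconditional sentence closes a bullet about monitoring for adverse effects, directly after a sentence about worsening, so reading it as deterioration on treatment is natural. A reader might infer that an admitted patient with a stable defect would be removed at once. That rests on one of three disagreeing sentences, and the other two would not remove the patient.

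A reader might also infer that the patients whose vision is in greatest danger would be enrolled and their surgery postponed. The documents do not rank this group's risk, and by definition its defect has been stable for at least 6 months. Immediate withdrawal with surgical referral and postponed surgery cannot both happen to the same patient. The protocol also states that the 4 weeks match its usual preparation time before standard care.

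**Conclusion.** The point holds as a conflict between passages. On a literal reading, Section 5.0 does not exclude chiasm compression with a field defect stable for at least 6 months, while Section 6.0 lists compression without any condition on the fields. Separately, the withdrawal statements disagree on whether a stable, pre-existing defect leads to withdrawal, and this affects every stable-defect patient whom Section 5.0 allows, with or without compression.

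The conflict covers one of nine status combinations between Sections 5.0 and 6.0, and three of nine between the exclusion list and the unconditional withdrawal sentence. These are counts of combinations, not of patients. The documents give no basis for estimating how many patients would be involved, and the number may be very small. A reader might take the lower power figures as the cost of this conflict. They hold only if the patient counts among the 16 without replacement, which the plan does not say.

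The conclusion assumes only that each line is read as written. It takes no view on which clinical rule is right. It is worth correcting because it sits on a safety boundary and the correction costs almost nothing.

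**What to change.** Reconcile the two visual lines in the Section 5.0 exclusion list, the Section 6.0 statement of who is excluded, the two sentences under Withdrawal of Subjects, and the Section 8.0 withdrawal rule. The test is simple: no combination of chiasm and field status should pass eligibility while meeting another exclusion or a withdrawal rule at entry. The nine-row table can serve as the check on the revised wording.

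State whether withdrawal refers to the absolute visual field or to change from the baseline field test. Use the same treatment of abutment and compression in Sections 5.0 and 6.0.

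Which patients are admitted and what triggers withdrawal are clinical decisions for the sponsor. The cost is an amendment to protocol wording. No new assessments are needed, since fields are already tested at screening, baseline and Day 29, and the sample size and decision rule stay as they are.

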## Section 6.0 Treatment of Subjects

Transsphenoidal pituitary tumor resection is the primary therapy for Cushing disease, and yields 30-70% surgical cure rates. Patients with recurrent or residual tumors, and/or are not surgical candidates typically undergo pituitary-directed radiation, adrenalectomy, treated with pasireotide, and/or medical suppression of adrenal gland cortisol production. In this study, we will treat patients with *de novo*, persistent, or recurrent Cushing disease with seliciclib during the period of evaluation and preparation for standard care, which usually takes 4 weeks at our center. We are excluding any subjects who need immediate surgical intervention, i.e. unstable visual field deficit, tumor compression of optic chiasm, or severe metabolic complications. We only will recruit those whom we would recommend for routine evaluation process for standard care. After completion of their participation in the study, subjects will be ready to start standard care. If a given patient responds to the study drug and chooses to stay on the drug after cessation of the trial, clinical data will continue to be collected for further analysis of drug response and monitoring safety.

Study calendar: baseline physical exam, vital signs, weight and laboratory evaluations will be conducted within 7 days prior to the start of therapy. Pituitary imaging and ECG will be performed within 60 days prior to the start of therapy. All procedures and evaluations may be performed within 3 calendar days of that specified in the protocol to accommodate patient convenience and scheduling. Patient informed consent will be obtained prior to any protocol-specific procedures. The schedule of study events is provided in Table 1.

Patients will be administered a dose of oral seliciclib 400 mg twice daily for 4 days every week for total of 4 weeks. Patients will be seen on days 1, 8, 15, 22 and 29 for repeat laboratory testing, assessment of treatment compliance, and toxicity according to National Cancer Institute Common Toxicity Criteria version 3.

The following tests will be performed:

### Screening visit: Day -60 to -1

- History and physical exam
- Dexamethasone dispensed
  - Dexamethasone will be dispensed during the screening visit. Study doctor will explain when the subject should take it. During an overnight dexamethasone suppression test, 8mg of dexamethasone will be taken orally the night before at 11:00 PM. Subjects will go to the local Quest laboratory the next morning and will have their blood drawn between 8:00 AM - 9:00 AM to test their serum cortisol levels. Dexamethasone, which acts like a cortisol, decreases the amount of ACTH released by the pituitary gland, which then decreases the amount of cortisol released by the adrenal glands. More than 50% suppression of morning cortisol level after dexamethasone administration will confirm the diagnosis of Cushing's disease. Patients who had previously undergone dexamethasone suppression test at Cedars-Sinai Medical Center or if the patient has been confirmed with diagnosis such as a previous surgery or IPSS a repeat exam is not required.
- 24 hour urinary free cortisol x 2
  - Subjects will be given 2 containers to collect 2 - 24 hour UFC
  - The 2 - 24 hour UFC can be collected anytime between one week after taking dexamethasone and the baseline visit
  - Subjects will drop off the 2 - 24 hour UFC at their local Quest laboratory

- ECG
- Visual fields
- Pituitary MRI
- HbA1C
- CBC with differential, CMP (including fasting blood glucose), LFTs
- Hormone profile: PRL, TSH, thyroid panel, free T4, IGF-1, LH, FSH, estradiol for females, testosterone (total and free) for males
- PT/INR
- Serum Pregnancy Test (for females of childbearing potential)
- Serum cortisol level at 8:00-9:00 AM on the day of screening visit, then at 8:00-9:00 AM the next day after an overnight 8 mg dexamethasone

#### Baseline visit 1: Day -7

- CBC with differential, CMP (including fasting blood glucose), PT/INR
- Fasting lipid profile, HbA1C, Hormone profile: PRL, TSH, adjusted T4, free T4, IGF-1, LH, FSH, estradiol for females, testosterone (total and free) for males,
- Plasma ACTH and serum cortisol levels (every three hours from 9:00 – 15:00)
  - Blood draws will be done via intravenous catheter every 3 hours from 9AM to 3PM.
    - In the case that an intravenous catheter cannot be placed, one blood draw will be performed at every 3 hour interval.
- Serum Pregnancy Test (for females of childbearing potential)
- ECG
- Visual fields
  - 2 x late night salivary cortisol collection at 23:00-24:00 PM on any nights between baseline visit 1 and visit 2. The subject will rinse their mouth thoroughly with water and discard (do not swallow). The subject will hold the Salivette(R) at the rim of the suspended insert and remove the stopper and remove the swab. The swab will be placed under the tongue until well saturated (approximately one minute). The subject will then return the saturated swab to the suspended insert and close the Salivette(R) firmly with the stopper.
- 24 hour urinary free cortisol x 3
  - Subjects will be given 3 containers to collect 3 - 24 hour UFC
  - The 3 - 24 hour UFC can be collected anytime between the baseline visit 1 and visit 2.
  - Subjects will drop off the 3 - 24 hour UFC at their local Quest laboratory

#### Visit 2: Day #1

- History and physical exam
- Serum Pregnancy Test (for females of childbearing potential)
- Plasma ACTH and serum cortisol levels (every three hours from 9:00 – 15:00)
  - Blood draws will be done via intravenous catheter every 3 hours from 9AM to 3PM.
    - In the case that an intravenous catheter cannot be placed, one blood draw will be performed at every 3 hour interval.
- 24 hour urinary free cortisol any time between days 3-7
  - Subjects will collect 3 - 24 hour UFC any time between days 3-7 prior to coming in for study visit 3

- 2 - late night salivary cortisol at 23:00-24:00 between days 3-7

Visit 3: Day #8

- History and physical exam
- Adverse events assessment
- CBC with differential, CMP (including fasting blood glucose), PT/INR
- Thyroid panel: TSH, adjusted T4, free T4
- Serum Pregnancy Test (for females of childbearing potential)
- Plasma ACTH and serum cortisol levels (every three hours from 9:00 – 15:00)
  - Blood draw will be done via intravenous catheter every 3 hours from 9AM to 3PM.
    - In the case that an intravenous catheter cannot be placed, one blood draw will be performed at every 3 hour interval.
- 
- ECG
- 24 hour urinary free cortisol any time between days 10-14
  - Subjects will collect 3 - 24 hour UFC any time between days 10-14 prior to coming in for study visit 4
- 2 - late night salivary cortisol at 23:00-24:00 between days 10-14
- 

Visit 4: Day #15

- History and physical exam
- Adverse events assessment
- CBC with differential, CMP (including fasting blood glucose), PT/INR
- Thyroid panel: TSH, adjusted T4, free T4
- Serum Pregnancy Test (for females of childbearing potential)
- Plasma ACTH and serum cortisol levels (every three hours from 9:00 – 15:00)
  - Blood draw will be done via intravenous catheter every 3 hours from 9AM to 3PM.
    - In the case that an intravenous catheter cannot be placed, one blood draw will be performed at every 3 hour interval.
- ECG
- 24 hour urinary free cortisol any time between days 17-21
  - Subjects will collect 3 - 24 hour UFC any time between days 17-21 prior to coming in for study visit 5
- 2 - late night salivary cortisol at 23:00-24:00 between days 17-21

Visit 5: Day #22

- History and physical exam
- Adverse events assessment
- CBC with differential, CMP (including fasting blood glucose), PT/INR
- Thyroid panel: TSH, adjusted T4, free T4
- Serum Pregnancy Test (for females of childbearing potential)
- Plasma ACTH and serum cortisol levels (every three hours from 9:00 – 15:00)
  - Blood draw will be done via intravenous catheter every 3 hours from 9AM to 3PM.
    - In the case that an intravenous catheter cannot be placed, one blood draw will be performed at every 3 hour interval.

- ECG
- 24 hour urinary free cortisol any time between days 24-28
  - Subjects will collect 3 - 24 hour UFC any time between days 24-28 prior to coming in for study visit 6
- 2 - late night salivary cortisol at 23:00-24:00 between days 24-28

Visit 6: Day #29

- History and physical exam
- Adverse events assessment
- CBC with differential, CMP (including fasting blood glucose), , PT/INR
- Fasting lipid profile, HbA1C
- Hormone profile: PRL, TSH, adjusted T4, free T4, IGF-1, LH, FSH, estradiol for females, testosterone (total and free) for males
- Serum Pregnancy Test (for females of childbearing potential)
- Plasma ACTH and serum cortisol levels (every three hours from 9:00 – 15:00)
  - Blood draw will be done via intravenous catheter every 3 hours from 9AM to 3PM.
    - In the case that an intravenous catheter cannot be placed, one blood draw will be performed at every 3 hour interval.
- ECG
- Visual Fields
- Pituitary MRI
- 24 hour urinary free cortisol on days any time between 30-35
  - Subjects will collect 3 - 24 hour UFC any time between days 30-35 prior to coming in for study completion visit
- 2 - late night salivary cortisol at 23:00-24:00 between days 30-35

Study Completion Visit: Day 36

- History and physical exam
- Adverse events assessment

Table 1. Study procedure flow sheet

Procedures	Screening Visit -60 to -1	Visit 1 Baseline	Visit 2 Day 1	Visit 3 Day 8	Visit 4 Day 15	Visit 5 Day 22	Visit 6 Day 29	Study Completion Visit
Standard of Care Procedures: Items, drugs and services that are part of regular care and would be done even if you did not take part in this research study. These will be billed to you and/or your insurance company.								
Visual Field Exam	X 							
MRI of the Pituitary	X 							
Research Related Procedures: Items, drugs and services done for research purposes only. These will be covered by the sponsor of the study and will NOT be billed to your insurance company.								
Review of medical records	X							
History and Physical Exam	X	X	X	X	X	X	X	X
Serum Pregnancy Test (for female of childbearing potential)	X	X	X	X	X	X	X	X
Blood Draw for blood count with differential, comprehensive metabolic panel (CMP), and prothrombin time/INR	X	X		X	X	X	X	
Thyroid panel (TSH, adjusted T4, free T4)				X	X	X		
Hormone profile (Prolactin, FSH, LH, estradiol for female, total and free testosterone for male, IGF-1, TSH, adjusted T4, free T4)	X	X					X	
Fasting lipid profile		X					X	
HbA1C	X	X					X	
Dexamethasone dispensed 	X							
Electrocardiogram (ECG)	X	X		X	X	X	X	
24 hour Urine Collection for free cortisol	X 	X 	X 	X 	X 	X 	X 	
Visual Field Exam		X					X	
Insertion of IV catheter peripherally for repeated blood draws		X	X	X	X	X	X	
Plasma ACTH and serum cortisol (every 3 hours from 9AM to 3PM)	X 	X 	X 	X 	X 	X 	X 	
MRI of the Pituitary							X	
Saliva sample for salivary cortisol		X	X	X	X	X	X	
Study drug dispensed 			X	X	X	X		
Adverse events assessment			X	X	X	X	X	X

1. If previously performed greater than 28 days from start of therapy, repeat exam will be RES.
2. If previously performed greater than 28 days from start of therapy, repeat exam will be RES.
3. Dexamethasone is taken one time the night of the screening visit. If previously performed at Cedars-Sinai Medical Center, or if the subject has been confirmed with diagnosis such as previous surgery or IPSS repeat exam is not required.
4. 2 - 24 hour UFC can be collected anytime between one week after taking dexamethasone and the baseline visit.
5. 3 - 24 hour UFC will be collected for 3 days prior to coming in for study visit.
6. Blood draws will be done only for cortisol level between 8:00-9:00 AM on the day of screening visit, and 8:00-9:00 AM the next day after 8 mg dexamethasone
7. Blood draws will be done via intravenous catheter every 3 hours from 9AM to 3PM. In the case that an intravenous catheter cannot be placed, one blood draw will be performed at every 3 hour interval.
8. Study drug is taken orally twice per day for 4 days each week.

